6.8. Publication Plan

The International Committee of Medical Journal Editors (ICMJE) member journals have adopted a trials-registration policy as a condition for publication. This policy requires that all clinical trials be registered in a public trials registry. The Sponsor will register the study and post-results as required by this policy.

It is the intent of the Sponsor that the multicenter results of this study will be submitted for publication (in a peer reviewed journal). A publications committee will be established to review the multicenter results and develop publications at the completion of the study. Individual Sites should coordinate requests for publication through the publications committee or the Sponsor.

7. Data Collection and Submission

The Clinical Data Management System (CDMS) for this study will be provided by:

7.1. Data Collection Methods

This study will report clinical data using a web-based application. The CDMS will be the database of record for the protocol and subject to regulatory inspections. All users will be trained to use the CDMS and will comply with study specific guidelines / instructions as well as applicable regulatory requirements.

Subject data will be collected using protocol-specific CRFs. Site staff will enter data directly into the CRFs for transmission to the Sponsor. The Sites will be notified of any significant amendments to the CRFs.

7.2. Data Clarification and Correction

Once entered, data will be evaluated to ensure that it is complete, consistent with related source documents and logically sound. If changes to the data in the CDMS are required, all changes, reasons for changes, and persons making the changes will be captured in the CDMS's audit trail.

The CRO is the coordinating center for data management for this Post-market study. The monitors will verify that all data entered into the CRFs are accurate against the source. Visual and computer error checks will be carried out as appropriate, and the investigative Site will be queried on errors concerning completeness and consistency of the data on the CRFs.

CONFIDENTIAL INFORMATION

Confidentiality of data shall be observed by all parties involved at all times throughout the Post-market study. All data shall be secured against unauthorized access.

7.3. CRF Completion Schedule

All CRFs including the AE CRFs should be completed on a regular basis and as soon as reasonably possible upon enrollment of the subject in the trial.

8. Risk Assessment

[REDACTED]

Risks associated with these devices including the GORE® VIABAHN® Endoprosthesis or the interventional procedure include, but are not limited to:

- Hematoma
- Stenosis
- Thrombosis
- Occlusion
- Distal embolism
- Side branch occlusion
- Vessel wall trauma
- Rupture
- False aneurysm
- Infection inflammation
- Fever
- Pain
- Deployment failure
- Migration
- Device failure
- Endoleak
- Open surgical conversion
- Death

Risks associated with the interventional procedure include, but are not limited to:

- Access site infection
- Entry site bleeding
- Hematoma
- Vessel thrombosis
- Occlusion
- Pseudoaneurysm

CONFIDENTIAL INFORMATION

- Trauma to the vessel wall (including rupture or dissection)
- Distal embolization
- Arteriovenous fistula formation
- Transient or permanent contrast induced renal failure
- Renal toxicity
- Sepsis
- Shock
- Radiation injury
- Myocardial infarction
- Fever
- Pain
- Malposition
- Malapposition
- Inflammation
- Open surgical conversion
- Death

8.2. Minimization of Risks

Potential risks associated with the use of the GORE® VIABAHN® Endoprosthesis may be minimized by the following activities:

- The Sponsor has performed qualification testing on the device and device components, and appropriate quality control measures have been implemented in production;
- Investigators will be selected who are knowledgeable and experienced in interventional radiology procedures, and vascular anatomy;
- The Site Investigator, Sub-Investigators, Clinical Study Coordinator(s) or designee at each Site will be trained to the protocol;
- Protocol inclusion / exclusion criteria are designed to select appropriate patients and identify potential complications;
- Data completed by the Sites will be monitored to evaluate protocol compliance, data accuracy and subject safety; and
- Safety and performance data obtained during the clinical study will be shared with the Site Investigators to aid understanding of the device and potential complications associated with its use.

However, there is no risk to the patient by participating in this retrospective study because the procedure has already been performed and no additional procedures are requested except hospital standard of care.

[REDACTED]

8.4. Risk-to-Benefit Rationale

CONFIDENTIAL INFORMATION

MD133246 Protocol Template
Revision#: 1
Doc Type: GC

This study does not lead to any change in patient management and patients will receive the same treatment as they would have received if they had decided not to participate. Therefore, there is neither an additional risk nor a direct benefit related to the participation in the study.

9. Adverse Events and Safety Monitoring

AEs are defined as any untoward medical occurrences, unintended disease or injury or any untoward clinical signs (including abnormal laboratory findings) in patients, users or other persons whether or not related to the investigational medical device.[56] According to the primary and secondary endpoints of this study, the documentation of adverse events will concern all serious adverse events and adverse events related to the initial study procedure or the study device, regardless of the severity throughout 36 months.

9.1. Anticipated Adverse Events

Anticipated AEs are complications that are known to be associated with patients undergoing endovascular PAA repair. See Section 8 Risk Assessment. Additional AEs may include: clinical sequelae associated with amputation, aneurysm enlargement, edema, dehiscence, vascular spasm, vascular trauma, coagulopathy, claudication, clinical sequelae associated with device fracture; stroke; non-improving wound; allergic reaction to the device or other components or perforation of the vessel.

9.1.1. Adverse Event Relationship

Each reported AE will be assessed by the Investigator for its primary suspected relationship to the device or procedure.

Only one primary relationship will be assigned to each reported AE. The relationships include: Study Device Related, Study Procedure Related, Not Related or an Unknown Relationship. Relationship descriptions are provided below:

- **Study Device Related:** The functioning or characteristics of the study device caused or contributed to the AE.
- **Study Procedure Related:** The initial study procedure (and not the device) caused or significantly contributed to the AE.
- **Not Related:** An AE which cannot be attributed to the study device or initial study procedure.
- **Unknown Relationship:** The relationship of the AE to the device or procedure cannot be determined.

9.1.2. Adverse Event Classification

Each AE will be assessed by the Investigator to determine if it is serious or non-serious.

Serious Adverse Event (ISO 14155 Definition)[56]

A SAE is an AE that:

- led to death
- led to serious deterioration in the health of the subject that either resulted in:
 - a life threatening illness or injury, or
 - a permanent impairment of a body structure or body function, or
 - inpatient or prolonged hospitalization, or

- medical or surgical intervention to prevent life threatening illness or injury or permanent impairment to a body structure or a body function
- led to fetal distress, fetal death or a congenital abnormality or birth defect.

SAEs include device deficiencies that might have led to a SAE if suitable action had not been taken or if an intervention had not been made or if circumstances had been less fortunate. Any planned hospitalization for pre-existing conditions, without serious deterioration in health, is not considered a SAE.

9.1.3. Adverse Event Reporting and Coding

AEs will be reported on the appropriate CRF for that visit and documented in the subject's permanent medical record. The Investigator at each Site is ultimately responsible for reporting AEs to the Sponsor. The Investigator shall supply the Sponsor with any additional requested information.

Timely and complete reporting of safety information assists the Sponsor in identifying any untoward medical occurrence, thereby allowing: (1) protection of safety of study patients; (2) a greater understanding of the overall safety profile of the GORE® VIABAHN® Endoprosthesis; (3) appropriate modification of study protocols; and (4) adherence to worldwide regulatory requirements.

The following information should be collected for each reported AE:

- AE Name
- AE Onset Date
- Relationship
- Classification (serious / non-serious)
- Treatment
- Outcome
- Resolution Date

All reported AEs will be coded using the Medical Dictionary for Regulatory Activities (MedDRA).

In reporting AEs the following submission guidelines should be followed:

- AE reporting begins once the subject has received a GORE® VIABAHN® Endoprosthesis and continues until study completion / discontinuation.
 - NOTE: Any AE that occurs while the subject is in the operating room / catheterization laboratory should not be recorded as an AE, unless it is unresolved when the subject leaves the operating room / catheterization laboratory.
 - NOTE: Any AE occurring after the final study visit will not be recorded in this study.
- AEs with an outcome status of "Ongoing" should be assessed at each follow-up evaluation to determine if the event has resolved. AEs ongoing at study completion / discontinuation should be left as "Ongoing" on the AE CRF.

CONFIDENTIAL INFORMATION

MD133246 Protocol Template

Revision#: 1

Doc Type: GC

- Clinical sequelae present at baseline should be recorded on the Medical History CRF. If the clinical sequela increases in severity or frequency from baseline then it should be reported as an AE.
- If known, the diagnosis of the underlying illness or disorder should be recorded, rather than its individual symptoms. If unable to provide a diagnosis, report the symptoms as separate events. AEs should be reported using the full name without abbreviations or narratives.
- If an event increases in severity (goes from a non-serious to a serious adverse event) then a stop date for the non-serious event should be provided and a new event with increased severity should be recorded.
- Subject death is not considered an AE. (See Section 9.1.4)
- A device fracture is not an AE but the clinical sequelae associated with the fracture should be recorded as an AE.
- PAA enlargement is an AE if it grows by more than 10 mm from the baseline measurement.
- Endoleaks
 - For type I, II and III endoleaks the possible relationship to the procedure or device will be based on the Investigators assessment as described in Section 9.1.1.
 - Type IV endoleaks should be considered related to the study device regardless of when the endoleak occurs.
 - Type V endoleaks should be classified as an unknown relationship.

All endoleaks should be reported as Adverse Events and the respective CRF pages need to be completed.

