3.3.2. Primary Endpoints

The primary performance endpoint for this trial is:

- Primary patency at 12 months.

The primary safety endpoint for this trial is:

- Serious adverse events and adverse events related to the study procedure or the study device at 12 months.

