#### 2.3.1.2 Primary Safety

The primary safety endpoint for this trial are serious adverse events and adverse events related to the study procedure or the study device at 12 months. An adverse event is any untoward medical occurrences, unintended disease or injury or any untoward clinical signs (including abnormal laboratory findings) in patients, users or other persons related to the investigational medical device or procedure. For this study, only device or procedure related adverse events need to be reported. A serious adverse event is an adverse event that led to death or lead to serious deterioration in the health of the subject that resulted in a life threatening illness or injury, or a permanent impairment of a body structure of body function, or in-patient or prolonged hospitalization, or a medical or surgical intervention to prevent life-threatening illness or injury, or permanent impairment to a body structure or a body function.

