### 5.4 Primary Endpoints

**Performance** will be evaluated by primary patency at 12 months of the GORE® VIABAHN® Endoprosthesis in the treatment of Popliteal Artery Aneurysms. A point estimate will be calculated requiring primary patency at the one year visit to be declared a success. Having loss of primary patency at day 365 will be tabulated as a failure. Primary patency is defined in section 3.3.1.

**Safety** of the GORE® VIABAHN® Endoprosthesis will be assessed through 12 months by evaluation of serious adverse events (SAEs) and adverse events related to the study procedure or the study device. Counts will be tabulated at 12 months.

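### Non-serious adverse events of unknown relationship, including non-serious Type V endoleaks, fall outside the safety counts, and most of them need not be collected

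*Protocol*

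**What the plan says.** **Endpoint.** Protocol 3.3.2 defines primary safety as "Serious adverse events and adverse events related to the study procedure or the study device at 12 months". SAP 5.4 assesses it by "evaluation of serious adverse events (SAEs) and adverse events related to the study procedure or the study device" and says only that counts will be tabulated. Protocol 10.3.5 and SAP 5.5 use equivalent wording for 24 and 36 months.

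**Relationship coding.** Protocol 9.1.1 states: "The relationships include: Study Device Related, Study Procedure Related, Not Related or an Unknown Relationship". It also states: "Only one primary relationship will be assigned to each reported AE". Unknown is defined as: "The relationship of the AE to the device or procedure cannot be determined".

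**Endoleaks.** Under Protocol 9.1.3, the investigator judges the relationship for Types I to III, Type IV is always device related, and "Type V endoleaks should be classified as an unknown relationship". The same section requires every endoleak to be reported as an AE.

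**Reporting scope.** SAP 2.3.1.2 says: "For this study, only device or procedure related adverse events need to be reported". Protocol 3.3.1 has the same rule. The opening of Protocol Section 9 says that "the documentation of adverse events will concern all serious adverse events and adverse events related to the initial study procedure or the study device".

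**AE definition.** Protocol 3.3.1 and SAP 2.3.1.2 define an AE as an occurrence related to the device or procedure. Protocol Section 9 defines it regardless of relationship.

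Neither document says how Unknown is handled in the safety counts.

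**The concern.** The endpoint divides non-serious events into related (counted) and everything else (not counted), but the coding scheme has a third possibility, Unknown. With no rule, the programmer will follow the wording and leave Unknown events out. This happens in the headline safety result of a single-arm study whose index procedures are all documented retrospectively.

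Type V endoleaks show the problem most clearly, because the coding rule removes investigator judgement. Protocol 1.3 gives excluding the aneurysm from blood flow as the device's purpose here, so a leak bears directly on performance. A Type IV leak of the same severity is counted.

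The reporting scope is the more serious half of the problem. An event that was collected but left out of a table can be put back. An event that was never entered on the case report form (CRF) cannot be, short of returning to the charts.

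**Working it through.** The documents give no safety rate, Type V rate or Unknown rate, so there is no plan figure to reproduce. The check is to follow each kind of event through the rules.

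| Event | Must it be collected? | In the primary safety count? |
|---|---|---|
| Non-serious, related | Yes | Yes |
| Non-serious, Type IV endoleak | Yes (9.1.3) | Yes, device related by rule |
| Non-serious, Type V endoleak | Yes (9.1.3) | No, Unknown by rule |
| Non-serious, Unknown, not an endoleak | Not required (3.3.1, Section 9, SAP 2.3.1.2) | No |
| Serious, Unknown | Yes, if Section 9 governs | Yes, if Section 9 governs; doubtful under 3.3.1 and SAP 2.3.1.2 |

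The last row is doubtful because Protocol 3.3.1 and SAP 2.3.1.2 make relatedness part of the AE definition and then define an SAE as a kind of AE. Read literally, a serious event of unknown relationship would then not be an SAE.

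**Direction.** Let S be the count of SAEs, R of non-serious related AEs and U of non-serious Unknown AEs. The plan's count is S + R. A count that includes Unknown is S + R + U. The difference is U, which is zero or more, so the omission can lower the count but never raise it.

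**Scale, for illustration only.** The inputs are n = 50 (Protocol 3.2: enrolment stops when 50 subjects have 12-month data) and an assumed base of 10 subjects with a qualifying event. Each subject whose only event is non-serious and Unknown is worth 1/50 = 2.0 percentage points. The intervals are exact (Clopper-Pearson) 95%.

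- Base: 10/50 = 20% (10.0 to 33.7)
- One such subject added: 11/50 = 22% (11.5 to 36.0)
- Two added: 12/50 = 24% (13.1 to 38.2)
- Three added: 13/50 = 26% (14.6 to 40.3)
- Five added: 15/50 = 30% (17.9 to 44.6)

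The step per subject is the same from any other base. The chance of at least one such subject in 50 is 1 − (1 − p)^50, where p is an assumed per-subject rate:

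- p = 1%: 39.5%
- p = 2%: 63.6%
- p = 5%: 92.3%
- p = 10%: 99.5%

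**The case against.** A reader might infer three stronger things, and the documents support none of them.

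1. **That every Type V endoleak is missed.** A serious one is counted if Section 9's scope of all SAEs governs. All must be reported, and they appear in the all-AE summary table (SAP 8.1) and in the all-AE and all-endoleak listings (SAP 8.2). A treated one reaches freedom from repeat intervention, because treatment of endoleaks is within the re-intervention definition. It may also count against primary patency, which requires no intervention. What remains is mainly a non-serious, untreated leak.
2. **That device-related harm is under-counted.** Unknown means that the link cannot be established, and a Type V leak has no known origin. The documents do not show that any omitted event is truly device related.
3. **That the plan treats Unknown as unrelated.** Not Related is its own category, and the SAP is simply silent on Unknown.

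It is also fair to say that the plan specifies counts and not a subject-level proportion, so the percentages above are not a planned statistic. No safety test or threshold is visible (the hypothesis and sample-size text is redacted), so no visible decision turns on this. Counting every Unknown event as related would be a convention that errs in the other direction. Finally, the reporting rule sets a minimum, so sites could enter Unknown events voluntarily.

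All of this narrows the point. It does not supply a rule for Unknown in the headline count. Voluntary entry would make collection uneven across sites, which is a poor basis for a sensitivity analysis.

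**Conclusion.** The point stands in a limited form. Following the plan as written leaves non-serious AEs of Unknown relationship, including non-serious Type V endoleaks, out of the 12-, 24- and 36-month safety counts. It also allows those that are not endoleaks to go unrecorded. The headline count may be understated by this route and cannot be overstated by it. The size is not available from the documents and may be zero. The 2 points per affected subject assumes a subject-level proportion with a denominator of 50, and it would be slightly smaller if more than 50 subjects are enrolled and analysed. What is affected is the interpretation of a descriptive safety result, not type I error or power. Whether serious Unknown events are counted depends on which AE definition governs, and the documents conflict on that.

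**What to change.** 1. In SAP 5.4 and 5.5, tabulate the safety counts in two rows: SAEs plus AEs that are related or of unknown relationship, and SAEs plus AEs known to be related. Showing both avoids attributing Unknown events to the device while keeping them in view.
2. In Protocol 3.3.1 and Section 9 and in SAP 2.3.1.2, extend the reporting scope to AEs that are related or of unknown relationship.
3. Reconcile the AE definition in Protocol 3.3.1 and SAP 2.3.1.2 (related only) with the one in Protocol Section 9 (regardless of relationship), so that serious events of unknown relationship are clearly counted.

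**Cost.** This takes a small protocol and SAP amendment, with the submissions to CCTIRS and CNIL and the site training that Protocol 6.5 requires. Charts already abstracted would need some re-review, and the safety figure may look less favourable.

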9.1.4. Subject Death

Death is not an AE but instead an outcome of an AE. In rare cases the known cause of death or one specific AE responsible for death may not be able to be declared as the major contributor to death. When possible, death should be an outcome and the underlying cause of the death recorded as an AE (e.g. cardiac arrest).

Any ongoing AE at the time of death will be indicated as ongoing on the CRF unless it is the single event that resulted in death of the subject.

9.2. Unanticipated Adverse Device Effects (UADE)

An UADE is defined in 21 CFR 812.3(s) as “any serious adverse effect on health or safety or any life-threatening problem or death caused by, or associated with, a device, if that effect, problem or death was not previously identified in nature, severity or degree of incidence in the investigational plan or protocol.”[59]

The Sponsor is required to notify FDA and French Health Authorities (Agence Nationale de Sécurité du Médicament et des Produits de Santé (**ANSM**)) of any UADE. Therefore, if a complication occurs that the Investigator believes may be a potential UADE, the Site should immediately contact the Sponsor to determine reporting requirements. In addition, when there is a reason to believe a device may have malfunctioned, causing potential harm to a subject, the Site should immediately notify the Sponsor.

CONFIDENTIAL INFORMATION

MD133246 Protocol Template

Revision#: 1

Doc Type: GC

The Investigator shall submit to the reviewing EC a report of any UADE occurring during an investigation as soon as possible, but in no event later than 10 working days after the Investigator first learns of the effect. All UADEs must be documented by the Investigator including the date of onset, a complete description of the event, possible reason(s) for the event, severity, duration, actions taken and outcome. Copies of all supporting documents should be submitted concurrently with the appropriate CRF.

A report from the Sponsor will be submitted to the FDA and participating Investigators within 10 working days after the Sponsor first receives notice of the effect.

10. Statistical Analysis

10.1. Study Objectives

The primary objective of the GORE® VIABAHN® Endoprosthesis Popliteal Artery Aneurysm study is to evaluate the safety and performance of the GORE® VIABAHN® Endoprosthesis for the treatment of patients with PAAs. The safety will be measured through evaluation of serious adverse events and adverse events related to the study procedure or the study device at 12 months. The performance will be measured through primary patency at 12 months.

[REDACTED]

10.3. Data Analysis

10.3.1. Timing of Analyses

An interim analyses of the primary endpoints and secondary endpoints (where possible) is planned for 12 month follow-up data after enrollment is completed. Complete analyses of the secondary endpoints will take place after the 36 month data for these patients are available. Patients that are lost to follow-up after their 12 month visit, will not be replaced, but any attempt will be made by the Investigator to document the reasons.

